Study Design	
Phase I/II study with three dosage levels of Ad5 [E1-, E2b-]-CEA(6D) vaccine (phase I component), and the Maximally Tolerated Dose (MTD) of Ad5 [E1-, E2b-]-CEA(6D) vaccine (phase II component). The study drug is Ad5 [E1-, E2b-]-CEA(6D) given by subcutaneous (SQ) injection every 3 weeks for 3 immunizations. The following procedures will occur:
 
1) Cohort 1: Three patients will receive Ad5 [E1-, E2b-]-CEA(6D) at a dose of 1×10^9 particles SQ in 0.5 mL every 3 weeks for 3 immunizations. Assessment of dose-limiting toxicities (DLT) for dose escalation will be made after all patients in this cohort have had a study visit at least 3 weeks after receiving their first dose of vaccine. If there are no DLT, defined as any Grade 2, 3 or 4 immediate hypersensitivity reactions, Grade 3 or 4 fever that may possibly be associated with the immunization, Grade ≥ 2 autoimmune events except for vitiligo or fever for less than 2 days and less than 101.5 °F, Grade ≥ 2 allergic reactions (grade 2 is defined as generalized urticaria as defined by NCI Common Terminology Criteria for Adverse Events (CTCAE version 4.0), or Grade ≥ 3 non-hematologic toxicity, then patients may begin enrolling into cohort 2. If there is 1 DLT, then an

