6. TREATMENT PLAN

Patients will be enrolled into successive dosage level cohorts of 3 or 6 patients and monitored for dose-limiting toxicity (DLT).

DLT (Based on NCI CTCAE version 4.0) is defined as any Grade 2, 3 or 4 immediate hypersensitivity reactions, Grade 3 or 4 fever that may possibly be associated with the immunization, Grade ≥ 2 autoimmune events except for vitiligo or fever for less than 2 days and less than 101.5 °F, Grade ≥ 2 allergic reactions (grade 2 is defined as generalized urticaria as defined by CTCAE version 4.0), or Grade ≥ 3 non-hematologic toxicity.

During dose escalation through the first three patients of cohort 3, there will be a minimum of 1 week between enrolling successive patients. The first patient will be called to check on their condition prior to enrolling the second patient since patients can be enrolled after 1 week of initiation of cohort 3. If no DLT have been observed at this point, then further enrollment can occur in cohort 3 and phase II component (Cohort 4) without the 1-week waiting period. Between dosage levels, through Cohort 3, assessment of DLT for dose escalation will be made after all patients in a cohort have had a study visit at least 3 weeks after receiving their first dose of vaccine and all the available safety data and laboratory results have been reviewed. Patients in cohort 5 may begin injections once all patients in cohort 4 have had at least their first injections and all patients in cohort 3 have had a study visit at least 3 weeks after receiving their first dose of vaccine. If DLT occurs in $<33\%$ of patients in a given dosage level cohort, progression to the next dosage level will proceed. If DLT occurs in $\geq 33\%$ of patients in a given cohort, the next lower dosage level will be defined as the maximum tolerated dose (MTD). If DLT occurs in $<33\%$ of patients in the highest dosage level tested, that dosage level will be defined as the MTD. In phase II (Cohort 4) and Cohort 5, if at any time the rate of DLT in patients enrolled is $\geq 33\%$, the MTD will be re-defined as the next lower dosage level. Additional details of this dose escalation and de-escalation plan are provided below and in Figures 3A, 3B and Table 3.

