- 6) Cohort 6: Up to ten (10) patients will receive Ad5 [E1-, E2b-]-CEA(6D) at a dose of 5×10^{11} particles SQ in 1.0 mL every 3 weeks for 3 immunizations. Patients will be permitted to receive booster doses of Ad5 [E1-, E2b-]-CEA(6D) every 3 months for a period of two years following the first 3 treatments. In the event that a qualified patient undergoes reimaging prior to the completion of their initial 3 study immunizations and is found to have disease progression, the patient should continue on the immunization protocol because this could be a “flare reaction” associated with the vaccine which may be an inflammatory response. Patients will be required to have MRI/CT scans performed prior to initiation of treatment, at 3 month intervals +/- 1 month for 12 months or if the investigator believes signs or symptoms are suggestive of progression or relapse. All patients will be followed for overall survival for a period of 24 months from initiation of treatment.
- 7) Patients will have 90 mL peripheral blood drawn prior to each immunization and approximately 3 weeks after the third immunization (Week 9) to determine whether there is an effect on the immune response at specific time points during the study and/or after a specific number of immunizations.
- 8) Time to progression will be measured using CT scans performed at approximately 3 month intervals (based on clinical standard of care).
- 9) For all patients, if scheduling conflicts arise, the scheduled 3-week interval between immunizations may be modified so that the interval between immunizations is between 20 and 28 days (3 weeks -1 day to 3 weeks +7 days). If the second and/or third immunization is delayed, the subsequent immunizations should occur no earlier than 20 days after the previous immunization.
- 10) The following safety events will trigger a temporary suspension of study vaccinations:
 - a) If one or more patients develop a Grade 4 allergic reaction without a clear attributable cause, other than study vaccine
 - b) Death not attributed to disease.

Assessment of these halting rules is a review of cumulative events for all study participants, and should not be confused with reasons for delaying or terminating the immunization schedule of any individual patient.

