6.1. Study Stopping Rules

- Death possibly related to the study agent.
- Two patients having a Grade 4 toxicity event that is possibly/probably related to the study agent.

Figure 3A.

[figure not shown]

Figure 3B.

[figure not shown]

Table 3. Calculation of rates of DLT during patient accrual in phase I and phase II

# evaluable for toxicity	Cohort 1 (n=3)	Cohort 2 (n=3)	Cohort 3 (n=6)	Cohort 4 (n=12)	Cohort 5 (n=6)	Cohort 6 (n=10)
# with DLT to be ≥33%	1	2	4	8	10	13

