7.3.2 Adverse Events

- 7.3.2.1 Toxicity will be graded according to the NCI Common Terminology Criteria for Adverse Events (CTCAE) version 4.0 (which can be downloaded from the CTEP web site (<http://ctep.cancer.gov>)). DLT is defined in Protocol Section 6.
- 7.3.2.2 Possible side effects from immunization may include local effects (pain, tenderness, redness or swelling), systemic effects (malaise, fatigue, myalgia, arthralgia, headache, nausea, vomiting, chills or fever), and allergic reactions such as hives, rash or anaphylactic reactions. Induction of auto-immunity, manifest as arthritis, serositis, nephritis, thyroiditis, colitis, neutropenia, etc., is theoretically possible, but has not been observed in our prior CEA vaccine studies. Also, liver function test abnormalities and liver failure are theoretically possible.

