7.3.3 Treatment of Toxicity

For acute allergic reactions, use of diphenhydramine 25-50 mg IV, corticosteroids (Solumedrol 100 mg), and epinephrine (1:1000, 0.3-1 mL sq) should be considered. These medications are available in the clinical setting where the vaccine will be administered. For auto-immunity, corticosteroids (prednisone 0.5-1 mg/kg/d) should be considered. Clinical assessment of other targets, such as thyroid, arthritis, urticaria, or proteinuria, for auto-immunity and serum sickness like antigen-antibody complex disease, will also be performed as indicated.

7.3.4 Active Immunotherapy will be Discontinued for:

- 7.3.4.1 Life-threatening anaphylactic reactions related to active immunotherapy
- 7.3.4.2 DLT related to active immunotherapy
- 7.3.4.3 Disease progression (by RECIST criteria). Patients will be offered referral to a medical oncologist for discussion of other treatment options, and for continued medical care.
 - 7.3.4.3.1 Disease progression prior to completing the 3 study immunizations:

In the event that a patient undergoes reimaging studies prior to the completion of their 3 study immunizations and is found to have disease progression, they will be permitted to continue on the study as long as the progression has been 50% or less by RECIST criteria.

If a patient is removed from the study prior to completion of the assigned vaccine schedule for any reason other than toxicity, that patient will be replaced, in order to obtain data to help determine the toxicity of the immunizations. We will allow up to 3 replacements per cohort (Phase I, Dose levels 1 and 2; Phase II, MTD).

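### One vaccine-related Grade 4 cytopenia that meets no other DLT criterion counts as zero DLTs and is not a listed toxicity reason to stop that patient's dosing

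*Combined protocol and SAP*

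**What the plan says.** All references are to the current version of the protocol, the one that adds cohort 6.

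- **DLT definition.** Section 6 lists immediate hypersensitivity, fever, autoimmune events and allergic reactions, and ends with "or Grade ≥ 3 non-hematologic toxicity". The Protocol Summary repeats this limit for cohort 1: "Grade ≥ 3 non-hematologic toxicity, then patients may begin enrolling into cohort 2". Neither place has a hematologic criterion at any grade.
- **Route by which some cytopenias do count.** The definition includes "Grade ≥ 2 autoimmune events except for vitiligo", and Section 7.3.2 describes possible autoimmunity as "manifest as arthritis, serositis, nephritis, thyroiditis, colitis, neutropenia, etc". An autoimmune neutropenia is therefore a DLT from Grade 2.
- **Stopping a patient.** The toxicity reasons in Section 7.3.4 are "Life-threatening anaphylactic reactions related to active immunotherapy" and "DLT related to active immunotherapy". DLT is also the only toxicity reason in Section 9.
- **Stopping the study.** Section 6.1 acts on a possibly related death, or on "Two patients having a Grade 4 toxicity event that is possibly/probably related to the study agent". The temporary halting rules in Section 6 cover a Grade 4 allergic reaction and a death not due to disease.
- **Safety verdict.** Section 8.1 calls a dose level safe if fewer than 33% of its patients have a DLT, and gives the limits as 0 of 3, 1 of 6, 3 of 12 and 5 of 18.

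**The concern.** Safety is the primary objective, and the DLT label does two jobs in this plan: it feeds the dose-level verdict and it triggers discontinuation in the individual. An event that misses the label misses both.

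The result is uneven. Generalized urticaria at Grade 2 is a DLT and ends that patient's dosing. A related Grade 4 cytopenia of the kind described does neither, although Section 10.6 places Grade 4 in the life-threatening or disabling band.

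Expected myelosuppression from study treatment does not explain the exclusion. Section 4.2.1 bars concurrent cytotoxic chemotherapy and requires at least 4 weeks since most prior therapy.

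What is at stake is mainly the next injection in the affected patient, and secondarily a dose-level decision that is already on its boundary.

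**Working it through.** **Step 1: apply each rule to the event.** Take one patient with a possibly or probably related, non-fatal Grade 4 cytopenia. It is not autoimmune, allergic or a hypersensitivity reaction, and there is no qualifying fever and no Grade 3 or higher bleed, infection or other non-hematologic complication.

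- Section 6 DLT definition: not met, count 0.
- Section 8.1: counts DLTs only, so the event is absent.
- Section 7.3.4, toxicity items: not met.
- Section 9, toxicity item: not met.
- Section 6 halting rules: not met (not allergic, not a death).
- Section 6.1: 1 of the 2 patients needed. The second patient's Grade 4 event must also be possibly or probably related, but it may be of any type.
- Section 7.3.1: removal is mandatory only if the patient starts chemotherapy, corticosteroids, other immunosuppressives or other immunotherapy.
- Re-dosing: blood counts are drawn at weeks 0, 3, 6 and 9 (Section 7.1.2), but Sections 6 and 7 set no count below which a dose is withheld. The thresholds in Section 4.1.7 apply at entry.

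**Step 2: reproduce the Section 8.1 limits.** Rate = DLTs / patients, compared with 33%.

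- 0/3 = 0%; 1/6 = 16.7%; 3/12 = 25.0%; 5/18 = 27.8%. All are below 33%, as the plan states.

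**Step 3: add the uncounted event.**

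- Alone in a larger group: 1/6 = 16.7%, 1/10 = 10.0%, 1/12 = 8.3%, 1/18 = 5.6%. No verdict changes.
- On top of a count already at its limit: 2/6, 4/12 and 6/18, each 33.3%. The verdict changes.
- In a three-patient cohort: 0/3 becomes 1/3 = 33.3%, which would call for three more patients. This concerns cohorts 1 and 2 only. An earlier protocol version already names the cohort 4 dose as the phase I MTD, which indicates that those cohorts are complete.

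**Step 4: a worked case in cohort 5.** One patient has a Grade 3 non-hematologic DLT and another has the cytopenia.

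- As written: 1/6, and 5×10^11 particles is declared the maximum feasible dose.
- With the cytopenia counted: 2/6, and 1×10^11 is declared the MTD.
- Section 6.1 is not met, because only one of the two events is Grade 4. Had both been related Grade 4 events, 6.1 would already have acted. The dose-level gap is therefore confined to one such cytopenia alongside DLTs that are not themselves related Grade 4 events.

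**Step 5: exposure left to the patient.** After dose 1 of 3, 3 − 1 = 2 primary doses remain, and the next may come as early as day 20. Cohort 6 adds optional boosters: "Patients will be permitted to receive booster doses". Quarterly boosting gives at most 12/3 = 4 under the one-year text in the Summary, or 24/3 = 8 under the two-year text in Section 6. That disagreement is a separate matter. These figures show what the rules permit; they do not measure harm.

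**The case against.** The strongest reply is that a single event of this kind would not go unnoticed. The serious-event definition in Section 10.5 covers life-threatening events and names blood dyscrasias among its examples of medically important ones. Section 10.8 sends serious, unexpected, possibly related events to the sponsor within 24 hours, and Section 10.9 adds 7-day and 15-day notices to the FDA. Through cohort 3, review of the available safety and laboratory data is required before escalation. Sections 8.1 and 10.5 commit to continuous safety monitoring. The investigator or sponsor may suspend vaccination for any safety concern. All of this stands, and it rules out the tempting reading that the plan has no control over such an event. None of these provisions, however, requires the next dose to be withheld: the review is mandatory, but the response is left to judgement.

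Second, the remaining event is narrow. Immune-mediated cytopenias already count, as do those with a qualifying fever or a serious complication. A reader might infer that cytopenias in general are ignored, or that the escalation decisions are unreliable; the documents support neither. No rate is given, so no probability can be attached.

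Third, Section 10.6 offers its grade descriptions as a general guideline. It does not show that every Grade 4 laboratory value is clinically life-threatening. That is fair, and it argues for a guarded fix.

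Fourth, the two-patient threshold in 6.1 may be a deliberate choice. As a rule for stopping the study it is defensible. It says nothing about whether the first affected patient should be dosed again.

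Fifth, cohort 6 has no cohort-specific DLT decision rule in Section 6, so there the gain from a fix is at patient level.

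**Conclusion.** The point holds in this limited form. Following the written rules, one related, non-fatal Grade 4 cytopenia outside the other DLT criteria counts as zero DLTs, is left out of the 8.1 tally and triggers no mandatory toxicity stop for that patient. Section 6.1 waits for a second patient with a related Grade 4 event.

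The consequence for the individual is that re-dosing is permitted, with 2 primary doses still scheduled if the event follows dose 1. At dose level one event alone changes nothing in groups of 6 or more; it matters only at the boundary (1/6 to 2/6, 3/12 to 4/12, 5/18 to 6/18).

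This rests on the event being judged related but not autoimmune, and on no steroid or other removal-triggering treatment being started. The documents do not say whether cohort 5 is complete, so its example may or may not still be live. A prudent investigator would probably stop anyway. The change is a cheap improvement that the sponsor should make, and the gap does not by itself call the dose findings into question.

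**What to change.** Add to the DLT definition, in Section 6 and in the Protocol Summary: *new or worsened-from-baseline Grade 4 hematologic toxicity possibly or probably related to the study agent*. The grade and attribution are those of Section 6.1, and the addition carries through to Sections 7.3.4.2 and 8.1 without further edits.

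Two details need settling:

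- The medical monitor should state whether isolated lymphopenia is exempt. Pretreated patients may enter with hemoglobin of 9 g/dL and platelets of 75,000, and there is no lymphocyte floor at entry; the new-or-worsened qualifier guards against counting what was present at baseline.
- Section 10.7 records causality only as yes or no, so the protocol should say which answer corresponds to possibly or probably related.

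If the sponsor prefers not to alter dose-level decisions, a line in Section 7.3.4 alone would close the patient-level gap but leave the boundary case in Section 8.1 open.

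The cost is one phrase in two places, using blood counts already drawn. A dose level may look slightly less favourable, and a three-patient cohort, if one is opened, may need three more patients. An affected patient loses the remaining doses. If that happens before dose 3, the patient is also not evaluable for immune response under Section 8.2 and, having left for toxicity, is not replaced under Section 7.3.4.

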	
Criteria for Adverse Events (CTCAE version 4.0), or Grade ≥ 3 non-hematologic toxicity, then patients may begin enrolling into cohort 2. If there is 1 DLT, then an additional 3 patients will be enrolled at this dosage level. Assessment of DLT for dose escalation will be made after the 3 additional patients have had a study visit at least 3 weeks after receiving their first dose of vaccine. If none of these latter 3 patients have DLT (i.e., 1 DLT in the 6 total patients), then patients may begin enrolling into cohort 2. If 2 patients have DLT at the lowest dosage level, dosing will be de-escalated to 1×10^8 particles.
 
3) Cohort 2: Three patients will receive Ad5 [E1-, E2B-]-CEA(6D) at a dose of 1×10^{10} particles SQ in 0.5 mL every 3 weeks for 3 immunizations. Assessment of DLT for dose escalation will be made after all patients in this cohort have had a study visit at least 3 weeks after receiving their first dose of vaccine. If there are no DLT, then patients may begin enrolling into cohort 3. If there is 1 DLT then an additional 3 patients will be enrolled at this dosage level. Assessment of DLT for dose escalation will be made after the 3 additional patients have had a study visit at least 3 weeks after receiving their first dose of vaccine. If none of these latter 3 patients have DLT, then patients may begin enrolling into cohort 3.
 
4) Cohort 3: Six patients will receive Ad5 [E1-, E2B-]-CEA(6D) at a dose of 1×10^{11} particles SQ in 0.5 mL every 3 weeks for 3 immunizations. Assessment of DLT for proceeding to phase II enrollment will be made after all patients in this cohort have had a study visit at least 3 weeks after receiving their first dose of vaccine. If there is 0 or 1 DLT, then patients may begin enrolling into the phase II portion of the study.
 
5) Phase II Cohort (Cohort 4): An additional 12 patients will receive Ad5 [E1-, E2B-]-CEA(6D) at the MTD every 3 weeks for 3 immunizations.
 
6) Cohort 5: Beginning after the third dose of ETBX-011 for the 12th patient in cohort 4, enrollment in an additional higher dose cohort will be permitted. Six patients will receive Ad5 [E1-, E2B-]-CEA(6D) at a dose of 5×10^{11} particles SQ in 2.5 mL every 3 weeks for 3 immunizations. Assessment of DLT will be made after all patients in this cohort have had all 3 injections and been observed for at least 30 days after the last injection. If there are 0-1 DLT, then this will be declared the maximum feasible dose. If there are 2 or more DLT, then 1×10^{11} particles will be declared the MTD.
 
7) Patients will have 90 mL peripheral blood drawn prior to each immunization and at week 9 to determine whether there is an effect on the immune response at specific time points during the study and/or after a specific number of immunizations.
 
8) Time to progression will be measured using MRI/CT scans performed as per standard of care (approximately 3 month intervals).

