6. TREATMENT PLAN

Patients will be enrolled into successive dosage level cohorts of 3 or 6 patients and monitored for dose-limiting toxicity (DLT).

DLT (Based on NCI CTCAE version 4.0) is defined as any Grade 2, 3 or 4 immediate hypersensitivity reactions, Grade 3 or 4 fever that may possibly be associated with the immunization, Grade ≥ 2 autoimmune events except for vitiligo or fever for less than 2 days and

less than 101.5 °F, Grade ≥ 2 allergic reactions (grade 2 is defined as generalized urticaria as defined by CTCAE version 4.0), or Grade ≥ 3 non-hematologic toxicity.

During dose escalation through the first three patients of cohort 3, there will be a minimum of 1 week between enrolling successive patients. The first patient will be called to check on their condition prior to enrolling the second patient since patients can be enrolled after 1 week of initiation of cohort 3. If no DLT have been observed at this point, then further enrollment can occur in cohort 3 and phase II component (Cohort 4) without the 1-week waiting period. Between dosage levels, through Cohort 3, assessment of DLT for dose escalation will be made after all patients in a cohort have had a study visit at least 3 weeks after receiving their first dose of vaccine and all the available safety data and laboratory results have been reviewed. Patients in cohort 5 may begin injections once all patients in cohort 4 have had at least their first injections and all patients in cohort 3 have had a study visit at least 3 weeks after receiving their first dose of vaccine. If DLT occurs in $<33\%$ of patients in a given dosage level cohort, progression to the next dosage level will proceed. If DLT occurs in $\geq 33\%$ of patients in a given cohort, the next lower dosage level will be defined as the maximum tolerated dose (MTD). If DLT occurs in $<33\%$ of patients in the highest dosage level tested, that dosage level will be defined as the MTD. In phase II (Cohort 4) and Cohort 5, if at any time the rate of DLT in patients enrolled is $\geq 33\%$, the MTD will be re-defined as the next lower dosage level. Additional details of this dose escalation and de-escalation plan are provided below and in Figures 3A, 3B and Table 3.

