- 3) Cohort 3: Six patients will receive Ad5 [E1-, E2b-]-CEA(6D) at a dose of 1×10^{11} particles in 0.5 mL SQ in the same thigh every 3 weeks for 3 immunizations. Immunizations site should be separated by 5 cm. A diary card will be given to each subject at the first treatment along with a ruler to record any adverse reactions for 2 days after treatment (24 hours and 48 hours post injection). The diary card will be placed in the study file. Assessment of DLT for proceeding to phase II enrollment (Cohort 4) will be made after all patients in this cohort have had a study visit at least 3 weeks after receiving their first dose of vaccine. If there is 0 or 1 DLT, then subjects may enroll in Cohort 4. If 2 patients have DLT at this dosage level, the dosage level in cohort 2 will be considered the MTD. If only 3 patients were enrolled in cohort 2, an additional 3 patients will be enrolled at that dosage before proceeding to the next level.
- 4) Phase II cohort (Cohort 4): After the MTD is established, an additional 12 patients will receive Ad5 [E1-, E2b-]-CEA(6D) at the MTD every 3 weeks for 3 immunizations.

Note: if during accrual of patients in the phase II cohort, DLT occurs at a sufficient rate such that the rate of DLT amongst the total number of patients (those treated at MTD in phase I and those in phase II) is $\geq 33\%$, then phase II will be restarted at the dosage level which is one level below the prior MTD.

- 5) Cohort 5: Six patients will receive Ad5 [E1-, E2b-]-CEA(6D) at a dose of 5×10^{11} particles SQ in 2.5 mL every 3 weeks for 3 immunizations. Assessment of DLT will be made after all patients in this cohort have had all 3 injections and been observed for at least 30 days after the last injection. If there are 0-1 DLT, then this will be declared the maximum feasible dose. If there are 2 or more DLT, then 1×10^{11} particles will be declared the MTD.

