6.2.2 How Supplied

ETBX-011 will be provided in a frozen state in a 2ml vial with a fill volume of 0.5 ml of extractable vaccine which contains 1×10^{11} total virus particles. The volume of injection for 1×10^{11} virus particles is 0.5 mL. The lower doses will be produced by dilution in 0.9% saline using the following directions. For cohort 6, ETBX-011 will be provided in a frozen state in a 2ml vial with a fill volume of 1.0 ml of extractable vaccine which contains 5×10^{11} total virus particles. The volume of injection for 5×10^{11} virus particles is 1.0 mL. The product should be stored at -20°C until used.

Instructions for dose preparation:

Cohort 1: To administer 1×10^9 virus particles by subcutaneous injection, perform 2 serial dilutions of vial vaccine as follows:

1. Draw 4.5 mL of sterile saline into a syringe.
2. Using a second syringe, withdraw 0.5 mL of previously thawed ETBX-011 from the supplied vial.
3. Remove the needle from syringe containing the 4.5 mL saline, and inject the 0.5 mL of ETBX-011 from the second syringe into the syringe containing saline.
4. Mix. This new solution has a concentration **2×10^{10} vp/mL**.
5. Use a new sterile syringe with a needle and repeat above procedure.
6. Withdraw 4.5 mL of sterile saline.
7. In the second syringe withdraw 0.5 mL from the syringe containing **2×10^{10} vp/mL**.
8. Remove the needle from the syringe containing the 4.5 mL saline, and inject the 0.5 mL of 2×10^{10} vp/mL from the second syringe.
9. Place a new needle on the 10-mL syringe from Step 8 above and mix the two solutions. This solution now has a concentration **2×10^9 vp/mL** (1×10^9 vp per 0.5 mL).
10. Label a new 1-mL sterile syringe ETBX-011, 1×10^9 vp and withdraw 0.5 mL from the syringe containing **2×10^9 vp/mL**. This prepared vaccine (**ETBX-011, 1×10^9 vp**) can be kept at room temperature for four hours prior to administering to the patient.

Cohort 2: To administer 1×10^{10} virus particles by subcutaneous injection:

1. Draw 4.5 mL of sterile saline into a syringe.
2. Using a second syringe, withdraw 0.5 mL of previously thawed ETBX-011 from the supplied vial.
3. Remove the needle from syringe containing the 4.5 mL saline, and inject the 0.5 mL of ETBX-011 from the second syringe into the syringe containing saline.
4. Mix. This new solution has a concentration **2×10^{10} vp/mL**.

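### The 1-week spacing between patients ends at the third cohort 3 patient and was not extended to cohort 5, the new highest dose

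*Combined protocol and SAP*

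**What the plan says.** All references are to the latest protocol version, the one that adds cohort 6, unless another is named.

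- **Stagger.** Section 6 (Treatment Plan): "During dose escalation through the first three patients of cohort 3, there will be a minimum of 1 week between enrolling successive patients". Provided no DLT has been seen by then, the wait is lifted for the rest of cohort 3 and for cohort 4. Cohorts 5 and 6 are not mentioned.
- **Doses.** Cohorts 1 to 3 receive 10^9, 10^10 and 10^11 particles in 0.5 mL. Cohort 4 is dosed at the MTD. Cohort 5 is six patients at 5×10^11 in 2.5 mL.
- **Opening of cohort 5.** Section 6: "Patients in cohort 5 may begin injections once all patients in cohort 4 have had at least their first injections", provided cohort 3 has also had its 3-week visits. Section 1 (Protocol Summary) opens it later, after the third dose of the twelfth cohort 4 patient. Neither sentence sets an interval between cohort 5 patients.
- **Review of cohort 5.** The formal DLT assessment waits until all six "have had all 3 injections and been observed for at least 30 days after the last injection". A running rule also applies: "In phase II (Cohort 4) and Cohort 5, if at any time the rate of DLT in patients enrolled is" 33% or more, the MTD moves down a level.
- **Cohort 6.** "Cohort 6: Up to ten (10) patients will receive" the cohort 5 dose in 1.0 mL. No spacing is stated.

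Appendix 1 (Schema) adds no spacing. The version that first introduced cohort 5 ("enrollment in an additional higher dose cohort will be permitted") already ended the stagger at the same patient.

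**The concern.** The sponsor spaced patients at each new highest dose up to 10^11. Cohort 5 is again a new highest dose, but the stagger sentence was carried forward unchanged when the cohort was added. A running DLT rule protects the next patient only if the previous patient has been observed first, and the stagger guarantees that. Without it, an acute reaction at the highest dose could occur in several patients before anyone could act on the first case.

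The automatic halting rules (Section 6) need a Grade 4 allergic reaction or a death not attributed to disease. The stopping rules (Section 6.1) need a related death or related Grade 4 toxicity in two patients. A Grade 2 or 3 DLT triggers neither.

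**Working it through.** The plan gives no figure for this point, so there is none to reproduce. The check is of the text first and then of the size of the effect.

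**Text.** The only spacing requirement ends at the third cohort 3 patient. Both opening conditions for cohort 5 refer to earlier cohorts. The minimum interval between cohort 5 first injections as written is therefore 0 days.

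**Dose.** Step: 5×10^11 / 1×10^11 = 5. Earlier steps: 10^10 / 10^9 = 10 and 10^11 / 10^10 = 10. Concentration: 1×10^11 / 0.5 mL = 2×10^11 per mL in cohort 3, and 5×10^11 / 2.5 mL = 2×10^11 per mL in cohort 5. Cohort 6: 5×10^11 / 1.0 mL, 2.5 times as concentrated.

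**Assumptions for the effect.** The acute DLT rate p after the first injection is not known, so 10%, 20%, 33% and 50% are shown. Patients are independent, every such DLT is known within 7 days, and dosing stops at the second DLT (the cohort 5 rule accepts 0 or 1). Under the stagger, patients 1 to 3 go one at a time. If none has a DLT, patients 4 to 6 may be dosed together; otherwise the spacing continues.

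**Permitted worst case** (comparator: all six dosed before any DLT is known). Dosing stops before the sixth patient with probability

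P(at least 2 DLTs in 5) − (1−p)^3 p^2.

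The subtracted term covers two DLTs in patients 4 and 5 after none in the first three, by which time patient 6 has already been dosed. At p = 0.10: 0.0815 − 0.0073 = 0.074. At p = 0.50: 0.8125 − 0.0313 = 0.781.

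Patients spared on average = p^2 + P(at least 2 in 3) + P(at least 2 in 4) + the probability above. At p = 0.10: 0.010 + 0.028 + 0.052 + 0.074 = 0.16. At p = 0.50: 0.250 + 0.500 + 0.688 + 0.781 = 2.22.

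**Planned pace.** Section 1 gives about 2 years in total, ending 6 months after the last enrolment, so accrual takes about 24 − 6 = 18 months, or 548 days. With 30 to 40 patients that is 548/30 = 18.3 to 548/40 = 13.7 days per patient. With random (exponential) arrivals, the chance that one gap is under 7 days is 1 − exp(−7/18.3) = 0.318 to 1 − exp(−7/13.7) = 0.400. The chance that at least one of the first two gaps is that short is 1 − (1 − 0.318)^2 = 0.535 to 1 − (1 − 0.400)^2 = 0.640. All six first injections fall within 7 days in only about 0.005% to 0.02% of cases. Cohort 5 with and without the stagger was simulated at this pace (200,000 runs, same stopping rule in both arms).

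| Assumed acute DLT rate | Spared, all six together | Stop before sixth with stagger, all six together | Spared, planned pace | Stop before sixth, planned pace: as written → with stagger |
|---|---|---|---|---|
| 10% | 0.2 | 7% | 0.03–0.04 | 7% → 8% |
| 20% | 0.6 | 24% | about 0.1 | 22–23% → 25–26% |
| 33% | 1.3 | 51% | about 0.2 | 47–49% → 52–53% |
| 50% | 2.2 | 78% | 0.3–0.4 | 74–76% → 80% |

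Patients queuing for cohort 5 to open would move the result from the planned-pace column towards the worst case. The documents give no basis for modelling that.

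**The case against.** The strongest reply is that ending the stagger was a defensible choice. The step to cohort 5 is the smallest in the trial and keeps the concentration. Up to 18 patients (6 in cohort 3 and 12 in cohort 4) will have been dosed at 1×10^11. Section 7.1.1 requires about 30 minutes in clinic after each injection, which covers immediate hypersensitivity, and 3 days of diary cards. Section 6 lets the investigator or sponsor suspend vaccination for any safety concern, and the 33% rule runs continuously. An intermediate version opened cohort 5 only on completion of cohort 4 and in the absence of DLT. Cohort 5 may have enrolled under that text; the documents do not say. The background is redacted and Figures 3A and 3B are not shown, so a rationale may exist.

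Most of this stands, and it limits the size of the point. It does not supply the missing interval. The observation and suspension provisions act after a patient has been dosed; none separates one first injection from the next. The stricter opening condition is absent from the latest version. After the clinic observation, no contact is scheduled for cohort 5 before the Week 3 visit; Section 6 asks for a call only to the first cohort 3 patient. Table 3 lists 10 DLTs as the 33% threshold for the six patients of cohort 5, which cannot be reached within that cohort.

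One could also argue that cohort 5 was never released from the wait, since the release names only the rest of cohort 3 and cohort 4. But the requirement itself ends at the third cohort 3 patient, so there was nothing to release.

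**Conclusion.** The gap is real, and closing it is a cheap improvement. The latest version sets no interval between patients at its highest dose, although the sponsor applied one at each earlier new dose level. The expected benefit is about 0.03 to 0.4 patients spared at the planned pace, and 0.2 to 2.2 in the permitted worst case. Both ranges rest on assumed DLT rates of 10% to 50%, onset within 7 days, and stopping at the second DLT.

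Three stronger readings are tempting, but the documents do not support them.

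- **That all six will be dosed together.** The text allows this but does not schedule it, and at the planned pace it is very unlikely. The figure of 2.2 patients is not the expected benefit.
- **That 16 patients (6 plus up to 10 in cohort 6) lack a stagger they should have had.** Cohort 6 repeats the cohort 5 total dose and is not dose escalation, so the sponsor's rule would not reach it. Its more concentrated fill makes a stagger there optional.
- **That the stagger was dropped without reason.** The visible text gives none, but part of the document cannot be seen.

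**What to change.** Amend the Section 6 sentence so that the spacing runs *through the first three patients of cohort 3 and the first three patients of cohort 5*. For cohort 5:

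- count at least 1 week between the first injections of successive patients;
- phone each patient before the next is injected;
- release the spacing 7 days after the third patient's first injection if there has been no DLT;
- keep the 1-week spacing for the rest of the cohort if there has been one.

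The same sentence may be applied to cohort 6 at the sponsor's choice.

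**Cost:** one sentence and a few phone calls. With no DLT, first injections fall on days 0, 7 and 14 and the rest from day 21, a delay of at most about 3 weeks and less at the planned pace. If spacing continues after a DLT, patients 4 to 6 follow on days 21, 28 and 35, about 2 weeks more.
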